
2. To further characterize and describe the proportion of participants in the Simultaneous and Sequential groups with local or systemic reactogenicity events of greater severity following each vaccination visit and cumulatively
	
2a. The proportion of participants reporting at least one moderate or greater or at least one severe or greater solicited local or systemic reactogenicity event in each vaccination group within 1-7 days following the first vaccination during which participants receive either IIV4 or placebo with an mRNA COVID-19 vaccine
 
2b. The proportion of participants reporting at least one moderate or greater or at least one severe or greater solicited local or systemic reactogenicity event in each vaccination group within 1-7 days following the second vaccination visit which participants receive either IIV4 or placebo
 
2c. The proportion of participants reporting at least one moderate or greater or at least one severe or greater solicited local or systemic reactogenicity event in each vaccination group within 1-7 days following the third vaccination visit during which all participants receive an mRNA COVID-19 vaccine alone for those receiving two doses of mRNA COVID-19 vaccine
 
2d. The proportion of participants reporting at least one moderate or greater or at least one severe or greater solicited local or systemic reactogenicity event in each vaccination group within 1-7 days following all vaccination visits combined

3. To describe the proportion of participants in Simultaneous and Sequential groups experiencing at least one unsolicited adverse event and one adverse event of special interest and to characterize these events	
3a. The proportion of participants in each vaccination group with an unsolicited adverse event occurring during the 7 days post each vaccination visit according to severity and system organ classification
 
3b. The proportion of participants in each vaccination group with an adverse event of special interest occurring during the study period according to event type

4. To compare the change of health-related quality of life (HRQOL) from baseline in the Simultaneous versus Sequential groups following the Vaccination Visit 1	4a. Comparison between vaccination groups of the mean maximal change in score from baseline on the EuroQOL 5 dimensions-5 level (EQ-5D-5L) and EuroQOL visual analogue scale (EQ VAS) within 1-7 days following the first vaccination visit

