5.1.1 Primary Two-Dose COVID-19 Series Schedule of Events

	Table 5: BNT162b2 (Pfizer-BioNTech) Schedule of Events										
Procedure	Visit 1	Visit 1a	Visit 2	Visit 2a	Visit 3 ¹	Visit 3a	Visit 3b	Visit 4 ²	Visit 5	Visit 6	Un-Scheduled
	Clinic	Phone/Text /Email/Data Review ^{3,4,5}	Clinic	Phone/Text /Email/Data Review ^{3,4,5}	Clinic	Phone/ Clinic	Phone/Text /Email/Data Review ^{3,4,5}	Clinic	Clinic	Phone	Clinic
Estimated Study Day (Relative to Visit 1)	1	1-7	8-15	8-15(+6)	29	22-57	22-57(+6)	36-43	50-85	121	
Time Following Visit 1 (Days) [Window]	0	0-6	7-14 [+2]		28 [+/-4]	21-56 [+/-4]				120 (+/-14)	
Time Following Visit 2 (Days) [Window]				0-6				28 [+/-4]			
Time Following Visit 3a (Days) [Window]							0-6		28 [+/-4]		
Informed consent & Medical Release of Information	X										
Review Eligibility Criteria	X										
Review Temporary Delay Criteria	X		X			X ⁶					
Demographic and Health History	X										
Influenza and COVID-19 Vaccination History	X										
Obtain unsolicited adverse events			X		X	X		X			
Obtain SAE and AESI information			X		X	X		X	X	X	X
Concomitant medications	X		X		X	X		X	X	X	X
Additional COVID-19 vaccinations										X	
HRQOL measure ⁷	X	X									
Measure temperature	X		X			X ⁶					X
Venipuncture	X				X			X	X		
Randomization	X										
Vaccination with COVID-19 vaccine	X ⁸					X ^{9,10}					

	Table 5: BNT162b2 (Pfizer-BioNTech) Schedule of Events										
Procedure	Visit 1	Visit 1a	Visit 2	Visit 2a	Visit 3 ¹	Visit 3a	Visit 3b	Visit 4 ²	Visit 5	Visit 6	Un-Scheduled
	Clinic	Phone/Text /Email/Data Review ^{3,4,5}	Clinic	Phone/Text /Email/Data Review ^{3,4,5}	Clinic	Phone/ Clinic	Phone/Text /Email/Data Review ^{3,4,5}	Clinic	Clinic	Phone	Clinic
Estimated Study Day (Relative to Visit 1)	1	1-7	8-15	8-15(+6)	29	22-57	22-57(+6)	36-43	50-85	121	
Time Following Visit 1 (Days) [Window]	0	0-6	7-14 [+2]		28 [+/-4]	21-56 [+/-4]				120 (+/-14)	
Time Following Visit 2 (Days) [Window]				0-6				28 [+/-4]			
Time Following Visit 3a (Days) [Window]							0-6		28 [+/-4]		
Vaccination with IIV4 or Placebo	X		X								
Memory Aid, Link to electronic symptom diary given to participant	X		X			X					
Assess for any immediate reactogenicity symptoms	X		X			X					
Electronic Diary Review ³		X		X			X				
Complete electronic or paper symptom diary ¹	X	X	X	X		X	X				

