- Participants/participant's LAR(s) complete electronic or paper solicited symptom diary each day at approximately the same time each day for days 1-7
- Participants/participant's LAR(s) using paper diary:
 - Study staff will call participants/participant's LAR(s) on days 2-4 following Visit

2 as a reminder to fill out the symptom diary on day 1-7 post Visit 2 regarding reactogenicity events and to bring the diary card to the next visit.

- Participants/participant's LAR(s) will be:
 - Asked to notify the study staff if they or their child is hospitalized or have a severe adverse event
 - Follow up with their or their child's healthcare if they have symptoms they find concerning
- Participants/participant's LAR(s) using REDCap web-based system:
 - Study staff will send reminders to fill out the symptom diary on day 1-7 post Visit 2 regarding reactogenicity events.
 - Study staff will review REDCap system to confirm data capture and assess for any AE or SAEs 2-4 days and 8-10 days following Visit 2
 - The study team will contact participants/participant's LAR(s) if they have any missing information. The study team may also contact participants/participant's LAR(s) if more information is needed to better describe AEs [including SAEs and severe (Grade 3) events] reported in the REDCap web-based system.
 - All participants/participant's LAR(s) using the REDCAP web-based system will be:
 - Asked to notify the study staff if they or their child is hospitalized or have a severe adverse event
 - Follow up with their or their child's healthcare provider if they have symptoms they find concerning

Visit 3 Study Day 29 (BNT162b2 or mRNA-1273) Clinic Visit

- Record any unsolicited AEs within the first 7 days post-vaccination, SAEs, AESI
- Obtain concomitant medication use
- Obtain 10mL blood sample for those \geq 12 year of age and 5mL blood sample for those 5-11 years of age prior to vaccination for serologic analysis (**Section 5.6.1**)
- Confirm date of next appointment

Visit 3a, Study Day 22-57 (BNT162b2) or 29-57 (mRNA-1273) Phone/Clinic Visit

- Review and confirm study eligibility and temporary delay criteria
- Record any unsolicited AEs within the first 7 days post-vaccination, SAEs, AESI
- Obtain concomitant medication use
- Obtain oral temperature

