Visit 4, Study Day 36-43 (BNT162b2 or mRNA-1273 vaccine) Clinic Visit

- Record any unsolicited AEs within the first 7 days post-vaccination, SAEs, AESI
- Obtain concomitant medication use
- Obtain 10mL blood sample for those \geq 12 year of age and 5mL blood sample for those 5-11 years of age prior to vaccination for serologic analysis (**Section 5.6.1**)
- Confirm date of next appointment

Visit 5, Study Day 50-85 (BNT162b2) or 57-85 (MRNA-1273) Clinic Visit

- Record any SAEs and AESI
- Obtain concomitant medication use
- Obtain 10mL blood sample for those \geq 12 year of age and 5mL blood sample for those 5-11 years of age prior to vaccination for serologic analysis (**Section 5.6.1**)

Visit 6, Study Day 121 Phone Visit

- Record any additional COVID-19 vaccinations since Visit 3a
- Record any SAEs and AESI
- Obtain concomitant medication use

Unscheduled Visits

- Obtain vital signs including oral temperature
- Review any solicited (\leq day 7) AEs submitted electronically, unsolicited AEs, SAEs, AESI, and concomitant medications (throughout period of enrollment)

5.1.2 Booster Dose mRNA COVID-19 Vaccine Schedule of Events**Table 7: Booster Dose Schedule of Events**

Procedure	Visit 1	Visit 1a	Visit 2	Visit 2a	Visit 3	Visit 4	Visit 5	Un-Scheduled
	Clinic	Phone/Text Email/Data Review ^{1,2,3}	Clinic	Phone/Text Email/Data Review ^{1,2,3}	Clinic	Clinic	Phone	Clinic
Estimated Study Day (Relative to Visit 1)	1	1-7	8-15	8-21	29	36-43	121	
Time Following Visit 1 (Days) [Window]	0	0-6	7-14 [+2]		28 [+/-4]		120 (+/-14)	
Time Following Visit 2 (Days) [Window]				0-6		28 [+/-4]		
Informed consent & Medical Release of Information	X							
Review Eligibility Criteria	X							
Review Temporary Delay Criteria	X		X					
Demographic and Health History	X							
Influenza and COVID-19 Vaccination History	X							
Obtain unsolicited adverse events			X		X	X		
Obtain SAE and AESI information			X		X	X	X	X
Concomitant medications	X		X		X	X	X	X
Additional COVID-19 vaccinations							X	
HRQOL measure ⁴	X	X						
Measure temperature	X		X					X
Venipuncture	X				X	X		
Randomization	X							
Vaccination with COVID-19 vaccine	X ⁵							
Vaccination with IIV4 or Placebo	X		X					
Memory Aid, Link to electronic symptom diary given to participant	X		X					
Assess for any immediate reactogenicity symptoms	X		X					
Electronic Diary Review ²		X		X				

Table 7: Booster Dose Schedule of Events

Procedure	Visit 1	Visit 1a	Visit 2	Visit 2a	Visit 3	Visit 4	Visit 5	Un-Scheduled

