Myalgia	Noticeable but does not interfere with activity	Some interference with activity but did not need a medical visit or absenteeism [i.e. missing work or school]	Significant; prevents daily routine activity and/or resulted in medical visit and/or absenteeism [i.e. missing work or school]	Requires an ER visit or hospitalization
Arthralgia	Noticeable but does not interfere with activity	Some interference with activity but did not need a medical visit or absenteeism [i.e. missing work or school]	Significant; prevents daily routine activity and/or resulted in medical visit and/or absenteeism [i.e. missing work or school]	Requires an ER visit or hospitalization
Chills	Noticeable but does not interfere with activity	Some interference with activity but did not need a medical visit or absenteeism [i.e. missing work or school]	Significant; prevents daily routine activity and/or resulted in medical visit and/or absenteeism [i.e. missing work or school]	Requires an ER visit or hospitalization

During Visits 2, 3, 4 participants/participant's LAR(s) will be encouraged to report any significant adverse events occurring within 7 days of the vaccination visits and during Visits 2, 3, 4, 5, and 6 any serious adverse events in an open-ended question format, e.g. "How are you or your child doing? Are you or your child having any medical or clinical problems? If so, please tell me about them." Participants/participant's LAR(s) who report severe solicited or unsolicited adverse events or express any concern about symptoms/unsolicited events will be encouraged to follow up with their or their child's primary care provider. Study staff will assist with coordination of referral appointments as necessary. Medical records will be obtained and reviewed for the occurrence of any adverse events, serious adverse events or adverse events of special interest throughout the study period.

Unsolicited adverse events (AEs) will be collected and reported for the 7 days following each vaccine visit. Serious adverse events (SAEs) and adverse events of special interest (AESI) will be collected and reported during the entire study period [i.e. from enrollment through 120 days following enrollment]. Unsolicited AEs, SAEs, and AESIs will be graded as follows.

Mild (Grade 1)	Moderate (Grade 2)	Severe (Grade 3)	Potentially Life Threatening (Grade 4)

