#### 3.3 Exploratory

- a) EOM1a: Comparison of the proportion of participants reporting at least one solicited reactogenicity event to include fever, chills, myalgia, or arthralgia of moderate or greater severity in the Simultaneous group with the Sequential group within 1-7 days following Vaccination Visit 3 during which all participants receive an mRNA COVID-19 vaccine alone for those receiving two doses of mRNA COVID-19 vaccine.
- b) EOM2a. The proportion of participants reporting at least one moderate or greater or at least one severe or greater solicited local or systemic reactogenicity event in each

vaccination group within 1-7 days following the first vaccination during which participants receive either IIV4 or placebo with an mRNA COVID-19 vaccine.

EOM2b: The proportion of participants reporting at least one moderate or greater or at least one severe or greater solicited local or systemic reactogenicity event in each vaccination group within 1-7 days following the second vaccination visit which participants receive either IIV4 or placebo.

EOM2c: The proportion of participants reporting at least one moderate or greater or at least one severe or greater solicited local or systemic reactogenicity event in each vaccination group within 1-7 days following the third vaccination visit during which all participants receive an mRNA COVID-19 vaccine alone for those receiving two doses of mRNA COVID-19 vaccine.

EOM2d: The proportion of participants reporting at least one moderate or greater or at least one severe or greater solicited local or systemic reactogenicity event in each vaccination group within 1-7 days following all vaccination visits combined.

c) EOM3a: The proportion of participants in each vaccination group with an unsolicited adverse event occurring during the 7 days post each vaccination visit according to severity and system organ classification.

EOM3b: The proportion of participants in each vaccination group with an adverse event of special interest occurring during the study period according to event type.

d) EOM4a: Comparison between vaccination groups of the mean maximal change in score from baseline on the EuroQOL 5 dimensions-5 level (EQ-5D-5L) and EuroQOL visual analogue scale (EQ VAS) within 1-7 days following the first vaccination visit.

e) EOM5a: To compare secondary outcomes 3a, 3b, 3c and 4a according to baseline COVID-19 serostatus.

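### In the primary series, unsolicited adverse events in the 7 days after COVID-19 dose 2 are not systematically asked about, although Exploratory outcome 3a reports them after each vaccination visit

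*Protocol*

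**What the plan says.** The commitment is the same throughout. Protocol Section 5.4 states: "Unsolicited adverse events (AEs) will be collected and reported for the 7 days following each vaccine visit". Exploratory outcome 3a in Protocol Section 2 is "The proportion of participants in each vaccination group with an unsolicited adverse event occurring during the 7 days post each vaccination visit", and SAP Section 3.3 repeats it as EOM3a.

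The enquiry is set out in three places:

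- Section 5.4 names the visits: "During Visits 2, 3, 4 participants/participant's LAR(s) will be encouraged to report any significant adverse events occurring within 7 days of the vaccination visits".
- In Tables 5 and 6, the row "Obtain unsolicited adverse events" is marked at Visits 2, 3, 3a and 4. It is not marked at Visit 3b, 5 or 6.
- The visit lists in Section 5.1.1 agree with the tables. At Visit 5 they record only serious adverse events (SAEs) and adverse events of special interest (AESI).

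The timing of the relevant visits is:

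- Dose 2: "Visit 3a, Study Day 22-57 (BNT162b2) or 29-57 (mRNA-1273) Phone/Clinic Visit"
- Last enquiry apart from the dose-2 contact: "Visit 4, Study Day 36-43 (BNT162b2 or mRNA-1273 vaccine) Clinic Visit"
- First visit timed from dose 2: "Visit 5, Study Day 50-85 (BNT162b2) or 57-85 (MRNA-1273) Clinic Visit"

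The notes to Tables 5 and 6 say that Visit 4 is timed from Visit 2, and they allow it on the same day as Visit 3a.

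**The concern.** Visit 4 is tied to the influenza or placebo injection at Visit 2, not to dose 2. When dose 2 is given close to Visit 4 or after it, no later scheduled visit asks about unsolicited AEs. Visit 5 always follows dose 2 by about four weeks, but its list leaves them out.

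Events that lead to medical contact may still reach the database by other routes. Grade 1 and 2 events, which by the protocol's grading need no medical visit, are the ones most likely to be lost. The reported proportion after dose 2 would then be too low, by an amount that depends on the dose interval and on whether the participant kept an electronic or a paper diary. SAP Section 8.3 (EO3) uses Full Analysis Population 2, that is, everyone randomized and vaccinated. It does not say how to treat participants who were not asked after dose 2.

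**Working it through.** **Inputs.** Tables 5 and 6 give Visit 2 at 7-14 days after Visit 1, Visit 4 at 28 days after Visit 2 (±4), Visit 3a at 21-56 or 28-56 days after Visit 1 (±4), and Visit 5 at 28 days after Visit 3a (±4). Visit 1 is Day 1.

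**Reproducing the plan's day ranges.**

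- Visit 2: 1 + 7 to 1 + 14 = Day 8-15.
- Visit 4: 8 + 28 to 15 + 28 = Day 36-43.
- Visit 3a: 1 + 21 to 1 + 56 = Day 22-57 (36 dates, BNT162b2), or 1 + 28 to 1 + 56 = Day 29-57 (29 dates, mRNA-1273).
- Visit 5: 22 + 28 to 57 + 28 = Day 50-85, or 29 + 28 to 57 + 28 = Day 57-85.

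All match the visit lists.

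**Coverage by Visit 4.** The vaccination day counts as Day 1 of the 7, so the period after a dose on day d ends on day d + 6. It has ended by Visit 4 if d + 6 ≤ Visit 4 day. That means d ≤ 30 when Visit 4 is on Day 36, and d ≤ 37 when it is on Day 43. Dose 2 falls on or after Visit 4 if d ≥ Visit 4 day.

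| Product | Visit 4 | 7 days ended by Visit 4 | Dose 2 on or after Visit 4 |
|---|---|---|---|
| BNT162b2 | Day 36 | 9/36 = 25% | 22/36 = 61% |
| BNT162b2 | Day 43 | 16/36 = 44% | 15/36 = 42% |
| mRNA-1273 | Day 36 | 2/29 = 7% | 22/29 = 76% |
| mRNA-1273 | Day 43 | 9/29 = 31% | 15/29 = 52% |

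**Sensitivity.**

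- If the period is taken to end on d + 7, the covered shares fall to 8/36 to 15/36 (22-42%) and 1/29 to 8/29 (3-28%).
- If every window is used to its limit, Visit 4 could be as late as 15 + 2 + 28 + 4 = Day 49. Coverage of the same dates then rises to 22/36 (61%) and 15/29 (52%). So the statement that most dates are not covered holds for the scheduled Day 36-43, but not at that extreme.

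**Groups that are covered.**

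- Children under 12 on BNT162b2 who keep to the 25-day limit in the notes to Table 5 have dose 2 on Day 22-26. Their 7 days end by 26 + 6 = Day 32, before Visit 4.
- Dose 2 at exactly 3 or 4 weeks is on Day 22 or 29. The 7 days end on Day 28 or 35, again before Visit 4.
- Booster participants have no dose 2 in the study. Their second injection is on Day 8-15, its 7 days end by 15 + 6 = Day 21, and their Visits 3 and 4 both come later.

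**With an enquiry at Visit 5.** Visit 5 falls 28 ± 4 = 24-32 days after dose 2. The 7 days have then ended for 36/36 and 29/29 dates.

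**The case against.** The strongest answer is that Visit 4 is not the only way to learn of these events.

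- At Visit 3b, staff review the REDCap record for any AE at 2-4 and 8-10 days, and may contact the participant about what they find. Electronic diaries are the preferred route.
- Section 5.4 has medical records reviewed for AEs throughout the study.
- Section 8.2 has the diary record any medical intervention sought.
- Unscheduled visits review unsolicited AEs.
- The sentence quoted from Section 5.4 goes on to an open question at Visits 5 and 6. It is aimed at SAEs, but as worded it could also draw out lesser problems.

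This stands, as far as it goes. A reader might infer that the outcome cannot be measured at all after dose 2, and the documents do not support that. But these channels are partial:

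- The REDCap review covers electronic users only, and the notes to Tables 5 and 6 describe the diary as one of solicited symptoms.
- The review text names Visit 3, which in the current schedule is a blood-draw visit without vaccination, so it has to be read as Visit 3a.
- Paper users get a reminder call at 2-4 days. When dose 2 is late, the next visit to which they bring the diary is Visit 5, which does not ask about unsolicited AEs.
- Medical records find only events for which care was sought.

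Four further objections limit the point:

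- A reader might take the percentages as shares of participants. The documents give no distribution of dose-2 dates, and Protocol Section 1.2 expects most adults and many children to be booster recipients.
- A reader might infer that participants who were not asked are counted as event-free. The SAP does not say so; it simply has no rule.
- The EO3 table counts participants with at least one unsolicited AE, so a missed dose-2 event changes that total only for someone with no other recorded event.
- The higher reactogenicity after dose 2 in Protocol Tables 1 and 2 concerns solicited symptoms, which the diary does collect after dose 2. It does not show that unsolicited events are more frequent then.

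**Conclusion.** The point holds as a gap in ascertainment. For primary-series participants, no scheduled visit asks about unsolicited AEs after the 7 days following dose 2 have ended, for 56-75% of permitted BNT162b2 dates (20/36 to 27/36) and 69-93% of permitted mRNA-1273 dates (20/29 to 27/29). This assumes Visit 4 on Day 36-43 and the period counted as dose day plus 6. The share of participants affected cannot be derived from the documents.

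The likely effect is that absolute rates after dose 2 are understated, chiefly for milder events for which no care was sought, and unevenly by diary type and dose interval. It would be tempting to read this as bias between the Simultaneous and Sequential groups. The documents do not show that: both arms follow the same schedule and both receive mRNA vaccine alone at that visit. The outcome is exploratory and descriptive, and no primary or secondary outcome depends on this enquiry. The change is still worth making, because the commitment is explicit and the remedy costs almost nothing.

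**What to change.** 1. In Tables 5 and 6, mark the unsolicited-AE row at Visit 5.
2. In the Visit 5 list of Section 5.1.1, add: record any unsolicited AEs within 7 days after the Visit 3a vaccination.
3. In Section 5.4, extend the sentence on reporting AEs to Visit 5 for the primary series, so that text, tables and visit lists agree.
4. For participants already past Visit 5, keep the denominator as it is. Report the dose-2 EOM3a proportion together with the number who had an unsolicited-AE enquiry after the 7 days had ended, and label it as incompletely ascertained. Restricting the denominator to those asked would select participants with short intervals and discard events found through REDCap or medical records.

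The cost is one cell in each of two tables, one line in a visit list, one amended sentence and one extra count in the report. No visit is added, since Visit 5 is already a clinic visit. The drawback is recall of 24-32 days. That is the interval over which Visit 4 already asks about Visit 2, although Visit 2 events are also asked about earlier, at Visit 3 (nominally 29 - 15 = 14 to 29 - 8 = 21 days after).

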With Day 1 serving as the initial day of vaccination, participants will be followed through Day 7 (total 7 days) for solicited symptoms of reactogenicity as described in Section 5.4. HRQOL data will be collected during this time period for persons aged ≥ 12 years. Solicited reactogenicity events will also be monitored through Day 7 (total 7 days) following Visit 2 (all participants) and Visit 3 (only those participants receiving primary 2-dose COVID-19 vaccine series). Participants will also be followed for 7 days after each vaccination visit for unsolicited adverse events, through Day 120 for serious adverse events (SAEs) and through Day 120 for adverse events of special interest (AESI), as described in Section 5.4.

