 - All participants/participant's LAR(s) using the REDCAP web-based system will be:
 - Asked to notify the study staff if they or their child is hospitalized or have a severe adverse event
 - Follow up with their or their child's healthcare provider if they have symptoms they find concerning

Visit 3, Study Day 29 Clinic Visit

- Record any unsolicited AEs, SAEs, AESI
- Obtain concomitant medication use
- Obtain 10mL blood sample for those \geq 12 year of age and 5mL blood sample for those 5-11 years of age prior to vaccination for serologic analysis (**Section 5.6.1**)
- Confirm date of next appointment

Visit 4, Study Day 36 - 43 Clinic Visit

- Record any unsolicited AEs, SAEs, AESI
- Obtain concomitant medication use
- Obtain 10mL blood sample for those \geq 12 year of age and 5mL blood sample for those 5-11 years of age prior to vaccination for serologic analysis (**Section 5.6.1**)

Visit 5, Study Day 121 Phone Visit

- Record any additional COVID-19 vaccinations since Visit 1
- Record any SAEs and AESI
- Obtain concomitant medication use

Unscheduled Visits

- Obtain vital signs including oral temperature
- Review any solicited (\leq day 7) AEs submitted electronically, unsolicited AEs, SAEs, AESI, and concomitant medications (throughout period of enrollment)

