**Table 2. Systemic Reactogenicity Grading (FDA modified)**

Systemic	Mild (Grade 1)	Moderate (Grade 2)	Severe (Grade 3)	Potentially Life Threatening (Grade 4)
Myalgia	Noticeable but does not interfere with activity	Some interference with activity but did not need a medical visit or absenteeism [i.e. missing work or school]	Significant; prevents daily routine activity and/or resulted in medical visit and/or absenteeism [i.e. missing work or school]	Requires an ER visit or hospitalization
Arthralgia	Noticeable but does not interfere with activity	Some interference with activity but did not need a medical visit or absenteeism [i.e. missing work or school]	Significant; prevents daily routine activity and/or resulted in medical visit and/or absenteeism [i.e. missing work or school]	Requires an ER visit or hospitalization
Chills	Noticeable but does not interfere with activity	Some interference with activity but did not need a medical visit or absenteeism [i.e. missing work or school]	Significant; prevents daily routine activity and/or resulted in medical visit and/or absenteeism [i.e. missing work or school]	Requires an ER visit or hospitalization

4. SO4: To describe the proportions of participants in the Simultaneous and Sequential vaccination groups experiencing at least one serious adverse event and a description of these events (tables 2 and 3 below).

A table will be produced that summarize participants experiencing at least one serious adverse event during the study period by vaccination group. This table will have the number and percentage of participants experiencing at least one serious adverse event by vaccination group and the 95% confidence interval of the difference between the vaccination groups. Listings with the clinical narratives will also be provided. The primary analysis population will be the Full Analysis Population 2.

Serious adverse events (SAEs) will be collected and reported during the entire study period [i.e. from enrollment through 120 days following enrollment]

A SAE is defined as an AE that meets one of the following conditions:

- Results in death during the period of protocol-defined surveillance
- Is life-threatening (defined as immediate risk of death at the time of the event)
- Requires inpatient hospitalization or prolonged hospitalization during the period of protocol-defined surveillance
- Results in congenital anomaly or birth defect
- Results in a persistent or significant disability/incapacity

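### The final safety call may fall 14 days before the end of the 120-day SAE and AESI period, leaving up to 14 days without scheduled ascertainment

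*Protocol*

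**What the plan says.** **The period.** Protocol Section 5.4 has SAEs and AESI "collected and reported during the entire study period [i.e. from enrollment through 120 days following enrollment". SAP Section 8.2 (SO4) repeats this for SAEs: "Serious adverse events (SAEs) will be collected and reported during the entire study period [i.e. from enrollment through 120 days following enrollment". SAP Section 8.3 (EO3) gives the same period for AESI. Protocol Section 3.1, which counts vaccination day as Day 1, follows participants "through Day 120 for serious adverse events (SAEs) and through Day 120 for adverse events of special interest (AESI".

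**The last contact.** The primary-series schedule ends with "Visit 6, Study Day 121 Phone Visit" and the booster schedule with "Visit 5, Study Day 121 Phone Visit". Tables 5, 6 and 7 all time this call at 120 (+/-14) days after Visit 1.

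**The contact before it.** For booster participants this is "Visit 4, Study Day 36 - 43 Clinic Visit"; for the primary series it is "Visit 5, Study Day 50-85 (BNT162b2) or 57-85 (MRNA-1273) Clinic Visit".

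**Other sources of events.** Section 5.4 also states: "Medical records will be obtained and reviewed for the occurrence of any adverse events", and extends this to SAEs and AESI over the study period. Participants sign a release of medical information at Visit 1, and unscheduled visits review SAEs and AESI. Participants are asked to tell staff about hospitalizations, but that request is listed under the 7-day diary periods.

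**The analysis.** SO4 and EO3 report the number and percentage of participants with at least one event per group, with a 95% confidence interval for the difference. There is no person-time adjustment.

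**The concern.** The outcome covers a fixed 120 days, but the schedule that feeds it may stop asking after 106. A participant called at day 106 is fully compliant, is not due to be contacted again, and enters the SAE and AESI proportions on the same footing as one called at day 120 or later.

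What is at stake is whether the stated safety window is actually delivered. AESI are the more exposed outcome. COVID-19 illness is on the AESI list in Section 5.4 with no severity or medical-care threshold, so a case can arise on any day and leave no record. SAEs usually generate a record, so they are better protected.

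**Working it through.** **Inputs.** The 120-day period (Protocol Sections 3.1 and 5.4; SAP Sections 8.2 and 8.3). The final-call window of 120 (+/-14) days after Visit 1 (Tables 5 to 7). Visit 2 at 7 to 14 days. Second mRNA dose (Visit 3a) at 21 to 56 days for BNT162b2 or 28 to 56 days for mRNA-1273. Booster Visit 4 is 28 days after Visit 2, and primary-series Visit 5 is 28 days after Visit 3a.

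**Step 1: reproduce the plan's study days** (study day = days after Visit 1, plus 1).
- Final call: 120 + 1 = Study Day 121, as stated.
- Booster Visit 4: 7 + 28 = 35 to 14 + 28 = 42 days after Visit 1, which is Study Day 36-43, as stated.
- Primary Visit 5: 21 + 28 = 49 (BNT162b2) or 28 + 28 = 56 (mRNA-1273), to 56 + 28 = 84 days, which is Study Day 50-85 or 57-85, as stated.

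**Step 2: range of the final call.** Earliest 120 - 14 = 106 days (Study Day 107); latest 120 + 14 = 134 days (Study Day 135). Follow-up by call varies by a ratio of 134/106 = 1.26.

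**Step 3: days of the period after the last scheduled contact** = max(0, 120 - call day).

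| Call, days after Visit 1 | Days left without scheduled ascertainment |
|---|---|
| 106 | 14 (14/120 = 11.7%) |
| 120 | 0 |
| 134 | 0 (and 14 days beyond the period are asked about) |

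**Step 4: what the call looks back over** (call day minus day of the preceding visit, nominal days).

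| Schedule | To a call at day 120 | To a call at day 106 |
|---|---|---|
| Booster | 78-85 days | 64-71 days |
| BNT162b2 primary | 36-71 days | 22-57 days |
| mRNA-1273 primary | 36-64 days | 22-50 days |

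These intervals hold no scheduled contact, but the call asks about them in retrospect. Only the days in Step 3 are exposed.

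**Step 5: average size, under assumptions.** The documents do not say when calls are made. If calls were spread evenly over the window, half would be early, by 7 days on average: 0.5 x 7 = 3.5 days, and 3.5/120 = 2.9% of planned follow-up. Assume further that no event in those days is caught by other means and that 1% of participants have an SAE. (Protocol Section 1.1 gives 1% for non-fatal SAEs in the mRNA-1273 trial, whose follow-up differs.) Then 450 x 0.01 x 0.029 = about 0.13 SAE missed in the whole study; at 2% it is about 0.26.

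**Side check.** Day 120 in Section 3.1, with vaccination on Day 1, is one day short of 120 days after enrollment, which is Study Day 121. The largest gap is 13 or 14 days depending on which is meant.

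**The case against.** The best defence is that the call is not the only source of events. Section 5.4 provides record review for SAEs and AESI over the study period, supported by the release signed at Visit 1, and unscheduled visits add to it. No text says the call closes surveillance. This largely answers the point for SAEs. It does not fully answer it for AESI, because no row or date in Tables 5 to 7 times the review to day 120 after an early call, and some AESI reach no record.

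The second argument is size. The expected loss is a fraction of one SAE, SO4 and EO3 are descriptive, and the window is identical in both blinded groups. All of that stands.

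The third is that a narrower window may lose calls. A booster participant with no final call loses the 78-85 days since Visit 4, against an average of 3.5 days under Step 5. Net follow-up would fall if completion dropped by more than 3.5/85 = 4.1% to 3.5/78 = 4.5%. This stands against halving the window. It has less force against moving it later at its present width.

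A reader might also infer three stronger things, none of which the documents support:
- **That the whole stretch after Day 36-43 or Day 50-85 goes unobserved.** The final call covers it retrospectively.
- **That the SAP has no limit for events reported at late calls.** SO4 and EO3 already define the period as ending at 120 days, so an event with onset on day 130 falls outside the outcome.
- **That myocarditis after a late second dose is specially at risk.** A dose at the latest permitted 56 + 4 = 60 days followed by a call at day 106 leaves 46 days covered, with Visit 5 about 28 days after that dose. The Protocol links myocarditis to the second dose but gives no onset time that would place it on days 46 to 60.

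**Conclusion.** The mismatch is real and minor. An in-window final call can leave up to 14 of 120 days (11.7%) of the stated SAE and AESI period without scheduled ascertainment. Record review and unscheduled visits reduce this without guaranteeing cover to day 120. The likely result is a small under-count and unequal follow-up in secondary outcome 4a and exploratory outcome 3b, more for home-managed COVID-19 illness than for SAEs. Because the schedule is the same in both blinded groups, the loss should be non-differential. The primary endpoint, measured in the 7 days after Visits 1 and 2, is unaffected.

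The 14-day maximum follows directly from the tables. The 3.5-day average and the 0.13 to 0.26 missed SAEs rest on evenly spread calls, no capture by other means, and an assumed SAE proportion of 1% to 2%.

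**What to change.** 1. In Protocol Tables 5, 6 and 7, do not allow the final call before day 120. Either 120 [0/+14], or 120 [0/+28] to keep the present 28-day width, would do.
2. For participants already called before day 120, state in Section 5.4 that the record review runs through day 120.
3. Record onset dates for SAEs and AESI. In SAP SO4 and EO3, apply the existing 120-day period as the cut-off by onset date and list later events separately.
4. Say once whether the last day is Study Day 120 or 121.

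**Cost.** Three table cells and a few sentences, with no added visit. The [0/+14] option halves scheduling flexibility and may lose some calls. The [0/+28] option keeps flexibility but allows calls up to day 148, so the longest nominal look-back for a booster participant rises from 134 - 35 = 99 to 148 - 35 = 113 days.
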